### 12.3 Statistical Analysis

The Vertex Biometrics Department or designee will analyze the safety and efficacy data.

The primary objective of this study is efficacy. The secondary objective is safety. This section summarizes the statistical analysis of efficacy and safety data. Methodological and related details (e.g., missing data) will be provided in the SAP.

The primary efficacy endpoint is the absolute change in  $LCI_{2.5}$  from baseline through Week 8. The objective of primary efficacy endpoint analysis is to demonstrate that the mean absolute change from baseline in  $LCI_{2.5}$  through Week 8 for subjects on TEZ/IVA excludes a pre-defined maximum placebo effect. The primary analysis of the primary efficacy endpoint will be based on a mixed-effects model for repeated measures (MMRM) with  $LCI_{2.5}$  at each time point as the outcome variable. The estimated mean change from baseline through Week 8 in  $LCI_{2.5}$  for subjects on TEZ/IVA along with the corresponding 95% CI will be provided. If the upper bound of the 95% CI is below the pre-defined maximum possible placebo effect, it will be interpreted as sufficient evidence to achieve the primary efficacy objective.

The study plans to enroll approximately 50 F/F subjects and up to 15 F/RF subjects.

A placebo group of F/F subjects and an IVA mono group of F/RF subjects will be included in this study. The main purpose is to preserve blinding, so that subjects and investigators do not assume a subject is receiving TEZ/IVA, which could introduce bias into the results. Descriptive statistics such as mean and SD will be provided for change from baseline in  $LCI_{2.5}$  at each post-baseline visit for homozygous subjects in the placebo group.

The target enrollment by genotype and treatment group is provided in the Table 12-1.

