##### **12.3.3.1 Analysis of Primary Variables**

The objective of primary efficacy endpoint analysis is to demonstrate that the mean absolute change from baseline in  $LCI_{2.5}$  through Week 8 excludes a pre-defined maximum placebo effect in subjects in the TEZ/IVA group. The primary analysis for the primary efficacy endpoint will be based on an MMRM using SAS PROC MIXED for the subjects in the TEZ/IVA treatment group in the FAS population. The MMRM will be used to estimate the within-group mean absolute change in  $LCI_{2.5}$  through Week 8 in the TEZ/IVA treatment group. The estimated mean change from baseline through Week 8 in  $LCI_{2.5}$  for subjects on TEZ/IVA along with the corresponding 95% CI will be provided. If the upper bound of the 95% CI is below the pre-defined maximum possible placebo effect, it will be interpreted as sufficient evidence to reject the null hypothesis.

The model will include absolute change from baseline in  $LCI_{2.5}$  (including all measurements up to Week 8 [inclusive], both on treatment measurements and measurements after treatment discontinuation) as the dependent variable, and visit (as a class variable) as a fixed effect, with adjustment for mutation group based on the second *CFTR* allele (F/F and F/RF) and baseline  $LCI_{2.5}$  value as fixed effects, and subject as a random effect. An unconstructed covariance structure will be used to model the within-subject errors.

Summary statistics (mean and SD) for change from baseline in  $LCI_{2.5}$  through Week 8, and at each visit will also be provided for subjects in the TEZ/IVA treatment group overall.

For homozygous subjects in the placebo treatment group, summary statistics (mean and SD) will be provided for change from baseline in  $LCI_{2.5}$  through Week 8, and at each visit.

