7.2 Sample Size and Power

The sample size of this study is driven by demonstrating that the treatment effect of TEZ/IVA excludes a maximum possible placebo effect, which is based on a within-group comparison (change from baseline in LCI_{2.5} in subjects on TEZ/IVA). If the corresponding 2-sided 95% CI of the change from baseline in LCI_{2.5} in subjects on TEZ/IVA excludes the pre-defined maximum possible placebo effect, it will be considered that the study has achieved its primary objective.

A placebo effect is not expected with LCI, because clinical data from other Vertex CFTR modulator studies consistently demonstrated a worsening of lung function (i.e., an increase from baseline in LCI) in the absence of CFTR modulator treatment. Study VX14-809-109 (Study 809-109) evaluated treatment with LUM/IVA in F/F subjects aged 6 through 11 years using change from baseline in LCI as the primary efficacy endpoint and provided the most relevant clinical LCI data available in the younger age group of CF subjects. In Study 809-

109, the placebo group had a mean worsening in LCI_{2.5} of 0.08 units with an SD of 1.41 (higher numbers indicate a worsening of an LCI measurement); the one-sided 90% lower bound was -0.10 and is used as an estimate for the pre-defined maximum possible placebo effect for Study 115.

Accounting for a 10% dropout rate, approximately 40 subjects in the TEZ/IVA group will provide at least 90% power to exclude -0.10 if the true mean change is -0.9 with an SD of 1.41 using a two-sided alpha of 0.05. The current estimate of the maximum possible placebo effect is based on Study 809-109 placebo data in pediatric F/F subjects with CF.

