9 STATISTICAL ANALYSIS

9.1 General Considerations

The Schedule of Assessments is provided in the clinical study protocol (CSP) Table 3-1. Individual subject data for subjects in the All Subjects Set will be presented in individual subject data listings. The precision standards are provided in [Appendix B](#).

Continuous variables will be summarized using the following descriptive summary statistics: the number of subjects (n), mean, standard deviation (SD), median, minimum value (min), and maximum value (max).

Categorical variables will be summarized using counts and percentages.

Baseline value, unless specified otherwise, will be defined as the most recent non-missing measurement (scheduled or unscheduled) collected before the first dose of study drug. For ECGs, the baseline value will be defined as the average of the non-missing pretreatment measurements (triplicate) on Day 1.

Absolute change from baseline will be calculated as Post-baseline value – Baseline value.

Relative change from baseline will be calculated and expressed in percentage as 100% × (Post-baseline value – Baseline value) / Baseline value.

Treatment-emergent (TE) Period will include the time from the first dose to 28 days after the last dose of the study drug or to the completion of study participation date, whichever occurs first. Completion of study participation is defined as one of the following:

- For subjects who complete the study and enroll in the extension study within 28 days of the Week 8 Visit: the last participation date
- For subjects who complete the study and do not enroll in the extension study within 28 days of the Week 8 Visit: the Safety Follow-up Visit
- For subjects who prematurely discontinue study drug treatment but do not withdraw consent: the latest of ETT Visit, or Safety Follow-up Visit (if required)
- For subjects who withdraw consent: date of withdrawal of consent

The TE period will be used for safety analyses unless specified otherwise.

Unscheduled visits: Unscheduled visit measurements will be included in analysis as follows:

- In scheduled visit windows per specified visit windowing rules.
- In the derivation of baseline/last on-treatment measurements.
- In the derivation of maximum/minimum on-treatment values and maximum/minimum change from baseline values for safety analyses.
- In individual subject data listings as appropriate.

Visit windowing rules: The analysis visit windows for protocol-defined visits are provided in [Appendix A](#).

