9.3.1 Analysis of the Primary Efficacy Variable

The primary efficacy endpoint is the absolute change in $LCI_{2.5}$ from baseline through Week 8. The objective of the primary efficacy endpoint analysis is to demonstrate that the mean absolute change from baseline in $LCI_{2.5}$ through Week 8 excludes a pre-defined maximum placebo effect in subjects in the TEZ/IVA group.

The primary analysis will be performed using a restricted maximum likelihood (REML)-based mixed-effect model for repeated measures (MMRM) for the subjects in the TEZ/IVA treatment group in the FAS population. The model will include absolute change from baseline in $LCI_{2.5}$ (including all measurements up to Week 8 [inclusive], both on treatment measurements and measurements after treatment discontinuation) as the dependent variable, and visit (as a class variable) as a fixed effect, with adjustment for mutation group based on the second *CFTR* allele (F/F and F/RF) and baseline $LCI_{2.5}$ (continuous) value as covariates, and subject as a random effect. An unconstructed covariance structure will be used to model the within-subject errors. If the model fails to converge, a compound symmetry covariance structure will be considered. The degrees of freedom of the denominator will be approximated by the Kenward-Roger's method².

The primary results obtained from the model will be the estimated average treatment effect through Week 8 in $LCI_{2.5}$ for subjects on TEZ/IVA. The corresponding LS mean, standard error (SE), 95% CI, and *p*-value will be provided. If the upper bound of the 95% CI is below the pre-defined maximum possible placebo effect, which was specified in the protocol, it will be considered that the study has achieved its primary objective. Summary statistics for change from baseline in $LCI_{2.5}$ through Week 8, and at each visit will also be provided for subjects in the TEZ/IVA treatment group by mutation groups and overall.

For F/F subjects in the placebo treatment group, summary statistics will be provided for change from baseline in LCI_{2.5} through Week 8, and at each visit.

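### The primary 95% CI comes from a baseline-adjusted model of one arm, and is too short for the population mean change whenever baseline LCI2.5 predicts change

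*SAP*

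**What the plan says.** SAP 9.3.1 and Protocol 12.3.3.1 fit an MMRM to TEZ/IVA subjects only, with visit, mutation group and baseline LCI2.5. The SAP lists the last of these among its adjustment terms ("continuous) value as covariates, and subject as a random effect") and uses Kenward-Roger degrees of freedom. The aim is a one-arm quantity: "The MMRM will be used to estimate the within-group mean absolute change". The decision rule is one-arm too: "If the upper bound of the 95% CI is below the pre-defined maximum possible placebo effect, which was specified in the protocol", the primary objective is met.

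The threshold is -0.10. SAP 7.2 takes it from another trial: "The current estimate of the maximum possible placebo effect is based on Study 809-109 placebo data in pediatric F/F subjects with CF". The same section claims at least 90% "power to exclude -0.10 if the true mean change is -0.9 with an SD of 1.41 using a two-sided alpha of 0.05".

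SAP 9.1 defines the outcome: "Absolute change from baseline will be calculated as Post-baseline value", minus the baseline value.

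The documents do not say whether the CI is meant only for the enrolled children's own baselines. They do not say how F/F and F/RF are weighted in the LS mean, and they give no correlation between baseline and change.

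**The concern.** A regression standard error is computed as if the covariate values were fixed. That matters little for a difference between randomized arms, because both arms share the slope and their mean baselines are close. Here one arm's adjusted mean is compared with a constant, so nothing cancels. Another sample of children would have a different mean baseline. If baseline predicts change, the mean change would move with it, and the model standard error does not count that movement.

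The slope is unlikely to be exactly zero. Because change is post-baseline minus baseline, measurement noise in the baseline alone produces a negative slope.

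This interval is both the success rule and the reported primary estimate. If it is too short, it covers less than 95%, and success is declared too often when the true change is at or just above -0.10.

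**Working it through.** **Inputs.** From SAP 7.2: true change -0.9, threshold -0.10, SD 1.41, two-sided alpha 0.05, 40 subjects, 10% dropout. From Protocol Table 12-1: 40 F/F + 12 F/RF = 52 on TEZ/IVA, or 36 + 11 = 47 after 10% dropout. Assumed: R² between baseline and visit-averaged change (within genotype) of 0 to 0.30, and LS-mean genotype weights equal to the observed proportions.

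**1. The plan's own figure.** Evaluable n = 40 × 0.9 = 36, so SE = 1.41/√36 = 0.235. Then 0.80/0.235 - 1.96 = 1.44, giving power of 92.6% (normal) or 91.1% (noncentral t). The stated 90% is reproduced, as a plain one-sample mean with the full SD of 1.41. The threshold fits the same picture: 0.08 - 1.282 × 1.41/√n = -0.10 solves to n of about 101. The documents do not give the placebo group's size, so that n is only back-calculated.

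**2. What the model SE omits.** With complete data, the LS mean at the mean baseline and observed weights is the raw arm mean.

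- Sampling variance: SD²/n
- Model variance: SD²(1 - R²)/n
- Omitted: b²·s_x²/n = R²·SD²/n

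The CI is therefore too short by the factor √(1 - R²), and the one-sided error at -0.10 is Φ(-1.96·√(1 - R²)). For R² = 0.10 this is Φ(-1.86) = 3.15%; for R² = 0.30, Φ(-1.64) = 5.05%. Kenward-Roger also conditions on baseline, so it does not restore the term.

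**3. Simulation of the model CI.** ANCOVA on averaged change with a genotype term, 40/12 subjects, SD 1.41, 100,000 trials per setting:

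| R² | Error at -0.10 | Coverage | False success at 0 |
|---|---|---|---|
| 0 | 2.4% | 95.1% | 0.7% |
| 0.05 | 2.8% | 94.5% | 0.8% |
| 0.10 | 3.2% | 93.7% | 0.9% |
| 0.20 | 3.8% | 92.4% | 1.2% |
| 0.30 | 4.9% | 90.3% | 1.6% |

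With b²·s_x²/n added and n - 3 df, error is 2.3% to 2.5%, coverage 95.1% to 95.4%, and false success at zero change 0.6% to 0.7%. If the genotypes differ by 1.5 SD in baseline, the pooled within-genotype variance still gives 2.3% to 2.4%; the total baseline variance over-corrects, to 1.9% at R² = 0.30.

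**4. Repeated-measures check.** REML MMRM with three visits, unstructured covariance, 10% monotone dropout, 40/12 subjects, 4,004 trials, n - 3 df without the Kenward-Roger adjustment (Monte Carlo SE 0.25 to 0.34 points). For R² = 0, 0.10, 0.20, 0.30, the error at -0.10 is 2.7%, 3.3%, 4.3%, 4.8% with the model CI, and 2.6%, 2.3%, 2.5%, 2.6% corrected.

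**5. Where the excess error lies.** At n = 52, SE = 1.41/√52 = 0.1955. The half-width should be 1.96 × 0.1955 = 0.383. The model gives 0.364 at R² = 0.10 and 0.321 at R² = 0.30, short by about 0.02 and 0.06. Error is therefore back to 2.5% at a true change of about -0.08 or -0.04 respectively. At -0.9 the two CIs lead to different decisions in 0.1% to 1.3% of trials.

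**6. Is R² > 0 plausible?** Suppose a share f of the change variance 1.41² = 1.988 is measurement noise, independent between visits, and true change is unrelated to true baseline. Then the noise variance per visit is σ_e² = f × 1.988/2, and for a single-visit change R² = σ_e⁴/(s_x² × 1.988).

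- f = 1, baseline SD 1.5: 0.994²/(2.25 × 1.988) = 0.22
- f = 0.5, baseline SD 2.5: 0.497²/(6.25 × 1.988) = 0.02
- f = 1, baseline SD 1.5, average of three visits: 0.994²/(2.25 × 0.994 × 4/3) = 0.33

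The baseline SDs and noise shares are assumptions; the documents give neither.

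**The case against.** The strongest reply is that nothing here is an error: the CI is valid conditional on the enrolled baselines, and conditional inference is ordinary regression practice. That is true, and the SAP's wording does not exclude it. But the plan is powered on the full SD and tests against a bound from another study's placebo sample, and both fit a population mean better. If the conditional target is intended, the SAP should say so.

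Second, the size depends on an R² that the documents do not give. At R² = 0 there is no defect, and a middle case of step 6 (baseline SD 2, 75% noise) gives about 0.07 for a single visit, hence an error of about 3%. This stands, and the figures should be read as a range.

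Third, the excess error occupies a narrow strip next to a threshold that is already cautious. This stands too: at a true change of +0.08, the placebo mean seen in the earlier study, false success is 0.2% to 0.5%.

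Fourth, 1.41 might be a residual SD. Corrected power would then be 95.0% (R² = 0.10) or 88.9% (R² = 0.30) at n = 47, and 88.0% or 78.9% at n = 36. However, SAP 7.2 gives 1.41 as the placebo group's SD beside its mean, which reads as a raw SD.

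Fifth, the planned overall mean and SD already allow a check: mean ± t × SD/√n has error 2.4% to 2.7%. That is a useful cross-check, but it is not the decision rule.

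Finally, the exact Kenward-Roger procedure was not simulated. That is a limit of the numbers. It does not change the argument, since the method conditions on baseline.

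**Conclusion.** The concern holds. As a 95% CI for the population mean change, the primary interval is too short whenever baseline LCI2.5 predicts change. For R² from 0.10 to 0.30 it covers about 94% to 90%, and one-sided error at -0.10 is about 3% to 5% instead of 2.5%. These figures assume 52 subjects, a total SD of 1.41 and observed genotype weights. With equal weights the model error is 2.5% to 4.2%.

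The practical reach is limited. False success with no true change stays below 2.5%, the planned decision at -0.9 would rarely differ, and the stated sample size is not wrong. The point is the accuracy of the primary interval. It should be corrected, with medium confidence in the size because R² is unknown.

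**What to change.** Keep the MMRM with visit, mutation group and baseline LCI2.5. In SAP 9.3.1:

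- Evaluate the LS mean at the sample-mean baseline.
- Base the decision CI on SE² + b²·s_x²/n, with b the estimated baseline slope, s_x² the pooled within-genotype baseline variance, n the TEZ/IVA subjects in the model, and n - 3 degrees of freedom.
- Report the current model CI as supportive.
- If inference only for the enrolled baselines is intended, say so and give the corrected CI as a sensitivity analysis.

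A separate point of specification: state the F/F and F/RF weights of the LS mean. Observed proportions match the planned overall summary (SAP 9.3.1: "and at each visit will also be provided for subjects in the TEZ/IVA treatment group by mutation groups and overall") and give about 98% corrected power at n = 52. Equal weights give 91.8% to 94.1% at n = 52 and 89.3% to 91.9% at n = 47. The choice is the sponsor's.

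The cost is two SAP sentences and a few program lines, with no extra subjects or data. Mean CI width goes from 0.782 to 0.790 at R² = 0 (about 1% wider), from 0.742 to 0.789 at 0.10 (6%), and from 0.654 to 0.787 at 0.30 (20%). At the SAP's assumptions with observed weights, corrected power is 97.9% at n = 52 and 96.6% to 96.7% at n = 47. At the 36 evaluable subjects behind the stated power, it is the 91.1% already computed for a plain mean.

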9.3 Efficacy Analysis

There is no multiplicity adjustment in this study; *P*-values provided for the secondary and other endpoints are considered nominal.

All efficacy analyses described in this section will be based on the FAS, unless otherwise specified. The analysis will include all available measurements through the last scheduled on-treatment visit, including measurements after treatment discontinuation.

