9.3.2 Analysis of Secondary Efficacy Variables

Absolute change in sweat chloride from baseline at Week 8

A similar MMRM model will be used for the above variable using the same approach as described for the analysis of the primary efficacy variable, with the addition of baseline sweat chloride as a covariate. The assessment of efficacy will be primarily based on the estimated mean change from baseline at Week 8.

Similar summary tables will also be provided using the same approach as described for the analysis of the primary efficacy variable.

Absolute change in the CFQ-R respiratory domain score from baseline through Week 8

A similar MMRM model will be used for the CFQ-R respiratory domain score based on the children's version, using the same approach as described for the analysis of the primary efficacy variable, with the addition of baseline CFQ-R respiratory score as a covariate.

Summary tables will also be provided for both the children's version and the parents/caregivers' version using the same approach as described for the analysis of the primary efficacy variable.

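### Does leaving the null for the primary p-value unstated put the -0.10 success rule at risk?

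*SAP*

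**What the plan says.** SAP 9.3.1 fits an MMRM to the TEZ/IVA group alone and lists the output for the average change in LCI2.5 through Week 8: "The corresponding LS mean, standard error (SE), 95% CI, and" a p-value. It gives neither the null value nor the sidedness of that p-value. The next sentence sets the success rule: "If the upper bound of the 95% CI is below the pre-defined maximum possible placebo effect, which was specified in the protocol", the primary objective is met. SAP 7.2 gives the value: "the one-sided 90% lower bound was -0.10 and is used as an estimate for the pre-defined maximum possible placebo effect for Study 115".

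Protocol 12.3.3.1 states the same rule and adds that, when it is met, "it will be interpreted as sufficient evidence to reject the null hypothesis". It does not write the null out, and it lists no p-value for the primary analysis. The study is powered against the same value, in the words of SAP 7.2: "90% power to exclude -0.10 if the true mean change is -0.9 with an SD of 1.41".

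For sweat chloride, SAP 9.3.2 says "A similar MMRM model will be used for the above variable", and it treats the CFQ-R respiratory score likewise. Neither has a reference value. SAP 9.3 says that p-"values provided for the secondary and other endpoints are considered nominal".

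**The concern.** The SAP adds a primary p-value that the protocol does not list, and leaves its null unstated. The success rule implies H0: mean change >= -0.10. But the secondary endpoints share the same modelling approach and have no reference value, so a p-value for them could sensibly test only no change. An analyst running one procedure for all three endpoints might test LCI2.5 against zero as well. The nominal label in SAP 9.3 covers only secondary and other endpoints, so such a p-value would carry no caution.

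At stake is how the result reads. In this single-group comparison, the -0.10 bound is what separates drug effect from placebo effect. A p-value against zero ignores that bound, looks stronger than the evidence for the actual claim, and could appear significant beside a failed primary objective. Two analysts could also report different primary p-values from the same data.

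**Working it through.** **Inputs.** Reference value -0.10, true mean -0.9, SD 1.41 and two-sided alpha 0.05 come from SAP 7.2. Evaluable n is 40 x 0.9 = 36 (SAP 7.2). If all TEZ/IVA subjects in Protocol Table 12-1 are counted, it is (40 + 12) x 0.9 = 46.8. The check uses a one-sample t approximation to the MMRM.

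**1. The plan's own power figure.** SE = 1.41/sqrt(36) = 0.235, and the critical t on 35 df is 2.030. The standardised distance from the reference value is (-0.9 + 0.10)/0.235 = -3.40. The noncentral t gives 91.1% power (normal approximation 92.6%), which agrees with the stated figure of at least 90%. The smallest n for 90% power is 35 against -0.10, or 35/0.9 = 38.9, so 39 enrolled. Against zero it would be 28, or 28/0.9 = 31.1, so 32. The planned 40 fits a null of -0.10.

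**2. The success rule is already a test against -0.10.** The rule LS mean + t x SE < -0.10 is the same as (LS mean + 0.10)/SE < -t. That is a two-sided p < 0.05 against -0.10 in the direction of benefit.

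**3. Where a p-value against zero would differ.** The critical estimate is -0.10 - t x SE for the rule and -t x SE for a test against zero. The gap is exactly 0.10 whatever the SE.

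| n | SE | t | Needed for success | Needed for p < 0.05 against zero |
|---|---|---|---|---|
| 36 | 0.2350 | 2.030 | below -0.577 | below -0.477 |
| 46.8 | 0.2061 | 2.013 | below -0.515 | below -0.415 |

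Example at n = 36 with an estimate of -0.50:
- against zero, t = -0.50/0.235 = -2.13 and p = 0.040;
- against -0.10, t = -0.40/0.235 = -1.70 and p = 0.098;
- the upper bound is -0.50 + 2.030 x 0.235 = -0.023, so the rule is not met.

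**4. How often the two disagree.** The chance is P(p < 0.05 against zero, favourable) minus P(success), both from the noncentral t.

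| True mean | n = 36 | n = 46.8 |
|---|---|---|
| -0.9 (design value) | 96.1% - 91.1% = 5.0% | 99.0% - 96.7% = 2.3% |
| -0.5 (illustrative, near the peak) | 54.3% - 38.0% = 16.3% | 66.1% - 47.6% = 18.5% |

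At a true mean of -0.10, a favourable p < 0.05 against zero occurs in 6.1% (n = 36) or 6.9% (n = 46.8) of trials, against 2.5% under the success rule.

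**5. Which null the text supports.** Protocol 12.3.3.1 ties the word null to the confidence-bound rule. SAP 9.3.1 states the aim of the analysis as excluding the maximum placebo effect. SAP 7.2 and Protocol 12.1 power the study to exclude -0.10. No section of either document sets out a test of LCI2.5 change against zero.

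**The case for a change.** The strongest case for a change is that nothing in the p-value sentence links it to -0.10, the SAP prevails over the protocol where they differ, and one added sentence would remove the doubt at almost no cost. Even in a successful trial, a p-value against zero would flatter the result: an estimate exactly on the success boundary has p = 0.05 against -0.10 but 0.019 (n = 36) or 0.016 (n = 46.8) against zero.

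The omission is real and the arithmetic stands. The inference drawn from it is weaker:

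- SAP 9.3.2 borrows its model from 9.3.1, not the reverse, and names no p-value or null. That other endpoints lack a reference value says nothing about the one endpoint that has one.
- The nominal label sits in the sentence on multiplicity. Leaving out the single primary endpoint is ordinary drafting and gives its p-value no role in the decision.
- The comparison of 6.1% to 6.9% with 2.5% describes a decision rule that the plan never uses, so it is not type I error inflation.
- The 16% to 19% figures need a true mean of -0.5, which appears nowhere in the documents.

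**Conclusion.** No change is needed. The null is implied rather than written beside the p-value, and the rest of the plan points to one value, -0.10. Because the primary objective is judged on the 95% confidence bound alone, an analyst who follows the text reaches the same estimate, interval, power (91.1% at n = 36), error rate (2.5% at a true mean of -0.10) and conclusion, whichever p-value is printed. If a p-value against zero were printed, it would part company with the success rule in about 2% to 5% of trials at the design value. The LS mean, SE and upper bound beside it would show the miss. Naming the null in the results table is normal reporting practice and does not require a revised plan.

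The figures assume an SE of 1.41/sqrt(n). The SD comes from the placebo group of Study 809-109, and the baseline-adjusted visit-average MMRM may give a different SE. That would move the band of disagreement and change its probability, but not its width of 0.10 or the success rule.
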